6.3 Measures to Minimize Bias: Study Intervention Assignment and Blinding

6.3.1 Study Intervention Assignment

Participants will be randomized in a 1:1 ratio to receive either Crinone® or the combination medication group on the day of ET.

The trial is designed as a single center trial, and randomization will be conducted on the ET day by using the block permutation method and stratified by age group (ages 20 to 35 years, or ages 35 years and over), which will guarantee that a balanced number of participants will be obtained between Crinone® and the combination medication groups inside each age stratum. If an error occurs (for example if the wrong list is used), the participant should continue with their assigned study intervention, and the next participant should still be assigned the next available number and study intervention of the correct list. The site must not attempt to “correct” for the error (i.e., if a participant is on the Crinone® list instead of the

combination medication group list, the site must not try to assign the Crinone® participant to the combination medication group list to offset this). Since ACCESS is an open-labeled observational study, baseline characteristic analysis will be presented to show whether the participants were well-stratified by age between the two study intervention groups.

6.3.2 Blinding

Not applicable

6.4 Study Intervention Compliance

See [Section 6.2](#) for dispensing and accountability of the study interventions.

Crinone® will be provided for free and Duphaston® will be prescribed by the physicians and will be bought by the participants themselves. Study intervention administration must be recorded in the CRF as applicable.

The acceptable compliance for this study is at a minimum of 80%.

6.5 Concomitant Therapy

Record in the CRF all concomitant therapies (e.g., medicines or nondrug interventions) used from the time the participant signs the informed consent until completion of the study, including any changes. For prescription and over-the-counter medicines, vaccines, vitamins, and herbal supplements, record the name, reason for use, dates administered, and dosing information.

Contact the Medical Monitor for any questions on concomitant or prior therapy.

6.5.1 Rescue Medicine

Rescue medications may be administered to address ineffective study intervention, anticipated adverse reactions or anticipated emergency situations.

Rescue medicine will be defined as the drug changed or dosage changed when the patient experiences threatened abortion. Rescue medicines will not be considered as prohibited medicines. Participants who use rescue medicines will be allowed to remain in the study.

6.5.2 Permitted Medicines

Medications that are considered necessary to protect the participant's welfare and will not interfere with the trial medication may be given at the Investigator's discretion.

Any medicines that are considered necessary to protect the participant's welfare in emergencies may be given at the Investigator's discretion, regardless if it results in a protocol deviation.

6.5.3 Prohibited Medicines

Other types of progesterone used one month before and during this study such as Utrogestan, intramuscular injections of progesterone; other ongoing vaginal medications. If any prohibited medicines are used, study participants will be allowed to remain on study provided that the Sponsor and the Investigator agrees. Rescue medicines are not considered prohibited medicines.

6.5.4 Other Interventions

Estradiol valerate will be administered according to local practice.

All participants will receive oral estradiol valerate continuously and the dose of estradiol valerate will be adjusted according to local practices.

6.6 Dose Selection and Modification

Not applicable.

6.7 Study Intervention after the End of the Study

The Sponsor will not provide any additional care to participants after they leave the study.

6.8 Special Precautions

Not applicable.

6.9 Management of Adverse Events of Interest

Refer to the package inserts for possible adverse drug reactions to Crinone® and Duphaston®. The management of adverse drug reactions should be based on the Investigator's judgment according to the medical condition of the participant.

7 Discontinuation of Study Intervention and Participant Discontinuation/Withdrawal

7.1 Discontinuation of Study Intervention

See [Section 7.2](#).

7.2 Participant Discontinuation/Withdrawal from the Study

A participant may withdraw from the study intervention and the study if any one or more of the below criteria are met:

- Adverse event (AE)/SAE, according to the discretion of the Investigator
- Participant is lost to follow up
- Withdraw consent

Participants will be informed that they have the right to withdraw from the trial at any time without prejudice to their medical care, and that they are not obligated to state their reasons for withdrawal. Participant data will be included in the analyses up until consent is withdrawn.

The trial exit electronic CRF will be completed when a participant is withdrawn from the trial. All withdrawals must be fully documented in the source documents.

A participant is considered having completed the observation period (i.e., not withdrawn from study intervention or study) when

- The participant achieves ongoing pregnancy

Or

- FET cycle may be considered finished when any one of the following applies:
 - β -hCG is negative (on the 13-15th day after ET)
 - Clinical pregnancy is negative (between the 4-6th week post-transfer)
 - Fetal heart beat stops before 10-12 weeks of pregnancy (8-10 weeks after ET).

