8.3.5 Pregnancy

Not applicable since ongoing pregnancy is the primary endpoint of the study.

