8.4 Study intervention Overdose

For this study, any dose of Crinone® greater than 90 mg/p.v./q.d in the single treatment group, or Crinone® at 90 mg/p.v./q.d and Duphasston® at 10 mg/p.o./b.i.d in the combination treatment group will be considered an overdose. The schedule can be seen in [Section 1.3](#). In case of an overdose, the participant will be assessed by Investigators as to whether they will continue participating in the study or not. Rescue medicines that are administered are not considered overdosing.

Even if it is not associated with an AE or a SAE, any overdose is recorded in the CRF and reported to drug safety in an expedited manner. Overdoses are reported on a SAE Report Form, following the procedure in [Appendix 3](#), section on Reporting Serious Adverse Events.

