After about 13 to 15 days of ET, early detection of pregnancy will be done by measuring β - β -hCG levels using blood tests and the results will be recorded.

The following data will be collected:

- Date of pregnancy assessment
- β -hCG test results (positive or negative)
- Details of luteal phase bleeding, if any
- Recording of AEs
- Concomitant medications prescribed and reasons.

If the result of the pregnancy assessment is negative, procedures related to End of Study visit will be performed.

Visit 5 (Clinical Pregnancy Assessment)

If the result of the β -hCG pregnancy assessment is positive, it will be further confirmed by a clinical pregnancy assessment (by means of an ultrasound examination) 4 to 6 weeks after ET.

The following data will be collected:

- Date of pregnancy assessment
- Pregnancy status
- Positive pregnancy status has to be confirmed by ultrasound examination (presence or non-presence of gestational sac(s), gestational sacs with or without heartbeat, gestational stage at which ultrasound is performed is to be recorded and ectopic pregnancy).
- Details of vaginal bleeding, if any
- Recording of all AEs, expedited reporting of all SAEs

- Concomitant medications prescribed and reasons.

If the result of the pregnancy assessment is negative, procedures related to End of Study visit will be performed.

Visit 6 (Ongoing Pregnancy assessment)

Ongoing pregnancy is defined as the presence of viable intra uterine fetus detected by ultrasound examination in 12 weeks of pregnancy. The following data will be collected:

- End of study intervention date
- Singleton pregnancy / multiple pregnancy
- Status of ongoing pregnancy
- Early miscarriage, if any
- Details of vaginal bleeding, if any
- Recording of AEs
- Concomitant medications prescribed and reasons.

If the status of ongoing pregnancy is confirmed negative, all procedures related to End of Study Visit will be performed.

If the status of ongoing pregnancy is negative and if it is due to an abortion - the reason for abortion should be recorded.

End of Study

The date and the reason of the completion/withdraw from study intervention or study (see [Section 7.2](#)) will be collected.

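### Women can be removed from the study by discretionary, open-label decision with no Visit 6 outcome required, so a continuing pregnancy can be scored as a primary-endpoint failure

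*Protocol*

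**What the plan says.** Protocol Section 7.1, headed "Discontinuation of Study Intervention", contains only a pointer to Section 7.2. Section 7.2 then treats leaving the drug and leaving the study together: "A participant may withdraw from the study intervention and the study if any one or more of the below criteria are met". Besides loss to follow-up and withdrawal of consent, it lists this ground: "Adverse event (AE)/SAE, according to the discretion of the Investigator". No severity threshold is given.

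Two other sections make staying in the study a matter of judgement:

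- Section 6.5.3, after use of a prohibited medicine: "study participants will be allowed to remain on study provided that the Sponsor and the Investigator agrees".
- Section 8.4, after an overdose: "the participant will be assessed by Investigators as to whether they will continue participating in the study or not".

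Rescue medicine, meaning a change of drug or dose for threatened abortion, is exempt from both rules, and women who use it stay in the study (Section 6.5.1).

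On exit, Section 7.2 asks for a trial exit form. The End of Study item in Appendix 4 lists "The date and the reason of the completion/withdraw from study intervention or study"; pregnancy status is not on the list. Section 8.3.5, on pregnancy in the safety system, reads "Not applicable since ongoing pregnancy is the primary endpoint of the study".

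On the analysis side, the SAP Section 14.1.1 denominator is every subject with an ET date. The numerator needs a positive result on the ongoing pregnancy page, and missing counts as failure. Protocol Section 9.4.2 has the same failure rule.

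**The concern.** Stopping study drug is not in itself the problem. Sections 1.2 and 4.1 say, directly after the sentence about women who discontinue study intervention, that follow-up runs until ongoing pregnancy is confirmed and/or the study ends. The SAP numerator has no on-drug condition. A woman who only stops drug is plausibly followed to Visit 6.

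The gap concerns a woman who is taken out of the study while still pregnant and has not withdrawn consent. Three sections allow this, none of them then asks for her 10–12 week outcome, and the analysis turns the empty field into a failure.

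The trial is open-label, so whoever decides knows the arm and, after the Day 14 test, knows whether the woman is pregnant. Losses of this kind cannot be assumed equal between arms. Each one also lowers the arm's own ongoing pregnancy rate. Section 9.4.3 makes that rate a primary output and says the analysis is meant to inform further trials.

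**Working it through.** **Following one woman through the text.** Suppose she has a positive clinical pregnancy assessment at Visit 5 and is then removed for an adverse event.

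1. Section 7.2 permits her removal from drug and study.
2. Her exit record holds a date and a reason.
3. The contact steps in Section 7.3 are triggered by failing to attend a required visit. Once out of the study she has none.
4. Section 8.3.3 follows ongoing serious adverse events to their outcome, which is not pregnancy status at 10–12 weeks. Section 8.3.5 sets up no separate pregnancy follow-up.
5. Under SAP Section 14.1.1 she is in the denominator and, with no Visit 6 result, counts as a failure. The backward imputation in SAP Section 14.2 is given for secondary endpoints only and needs a later positive result.
6. SAP Section 14.2 scores missing early abortion as not occurred. She is therefore counted as having neither an ongoing pregnancy nor an early abortion.

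**Inputs for the size.** The plan has 334 participants (Section 4.1) at 1:1 (Section 6.3.1), taken here as 167 per arm. The sample-size section is redacted, so 334 is used as given and cannot be reproduced. Ongoing pregnancy rates of 40–50% are assumed; the 40% cited in Section 2.2 is a clinical pregnancy rate. No exit rate is given.

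**Shift per woman.** 1/167 = 0.599 percentage points.

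**Precision of the difference.** The 90% Wald half-width is 1.645 × √(2p(1−p)/167):

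- p = 0.40: 8.82 points
- p = 0.50: 9.00 points

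Unstratified Miettinen–Nurminen intervals agree: (−8.81, 8.81) for 67/167 v 67/167, and (−8.98, 8.98) for 83/167 v 83/167.

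**Net excess k of lost ongoing pregnancies in one arm.** Shift = k × 0.599:

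| k | Shift (points) | Share of 90% half-width |
|---|---|---|
| 1 | 0.6 | 7% |
| 2 | 1.2 | 13–14% |
| 3 | 1.8 | 20% |
| 4 | 2.4 | 27% |

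At k = 3 the Miettinen–Nurminen interval becomes (−10.55, 6.99) for 64 v 67, and (−10.76, 7.19) for 80 v 83. About 15 net women would be needed to equal the half-width (8.82/0.599 = 14.7; 9.00/0.599 = 15.0).

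**Effect on an arm's own rate.** The Clopper–Pearson 95% interval is 32.6–48.0% for 67/167 (half-width 7.7 points) and 41.9–57.5% for 83/167 (half-width 7.8 points). If a share s of an arm's 67–83 ongoing pregnancies is lost this way, the rate falls by s × p:

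- s = 1%: 0.4–0.5 points
- s = 2%: 0.8–1.0 points
- s = 5%: 2.0–2.5 points

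These shares are a range to scan, not estimates, and the low end is the more plausible. With equal true rates, equal removal and equal chance of continuing pregnancy in both arms, the difference does not move, but both arm rates still fall.

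**The case against.** The strongest reply is that the protocol already intends to follow everyone. The follow-up sentence in Sections 1.2 and 4.1 is general, Section 4.4 ends the study with the last participant, and Section 7.2 adds: "Participant data will be included in the analyses up until consent is withdrawn". A woman removed for an adverse event has not withdrawn consent, and nothing says outcome collection stops for her. Sections 6.5.3 and 8.4 allow removal but do not order it. The likeliest trigger, threatened abortion, falls under the rescue exemption. A woman still pregnant in an artificial cycle depends on exogenous progesterone (Section 2.2) and would be expected to stay in care, where a scan could be recorded. The trial is an exploratory pilot with no confirmatory test, and the likely shift is well inside the confidence interval.

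Much of this stands and limits the size of the point: the routes are narrow, the protocol describes both drugs as well tolerated (Section 2.3), and no exit rate supports a large figure. It does not close the gap. The follow-up sentence is worded with and/or and does not say that a woman taken out of the study still attends Visit 6, whereas Section 7.2, the specific rule, provides for her leaving. The sentence on data use governs data already held and does not require new collection. Routine care may produce a scan, but nothing requires its result to reach the case report form.

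**Conclusion.** The concern holds. Every link is in the text: discretionary exit that couples drug and study, no outcome required afterwards, and an analysis that scores the missing result as failure. An analyst cannot recover an outcome that was never collected.

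With 167 per arm and rates of 40–50% assumed, each affected woman costs her arm 0.6 points. The error in each arm's rate from this source is always downward. The effect on the difference depends on the net imbalance between arms, and neither its size nor its direction can be derived from the documents. It is probably small. The change is still worth making because the loss is avoidable, falls on the primary endpoint and is cheap to prevent. Confidence is medium, since the follow-up sentence in Sections 1.2 and 4.1 can be read more generously.

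**What to change.** - **Section 7.1:** state that stopping one or both study drugs for any reason, including an adverse event at the investigator's discretion, is not withdrawal from the study. Pregnancy status through Visit 6 is still collected unless the woman withdraws consent to follow-up or is lost.
- **Section 7.2:** apply the adverse event ground to study intervention only, with outcome follow-up continuing.
- **Sections 6.5.3 and 8.4:** keep the clinical decision on whether study drug continues, record the event as a protocol deviation, and continue outcome follow-up.

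The rescue-medicine rule and the SAP's rule that missing counts as failure stay as they are.

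The cost is wording in four sections and a few follow-up contacts with women who are off drug. No new visit, test or case report form field is needed: Visits 4–6 and the ongoing pregnancy page exist, and Appendix 4 procedures follow the site's routine practice. The amendment needs ethics committee approval and, if the consent form is updated, re-consent of current participants (Appendix 2). The investigator keeps control of study drug but can no longer end outcome follow-up because of an adverse event, an overdose or a prohibited medicine. Where the Visit 6 result is then obtained for every removed woman who has not withdrawn consent, bias from this source is zero. The planned number and the precision are unchanged.

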7.3 Lost to Follow-Up

A participant will be considered lost to follow-up if he or she repeatedly fails to return for scheduled visits and is unable to be contacted by the study site.

The following actions must be taken if a participant fails to return to the clinic for a required study visit:

- The site must attempt to contact the participant and reschedule the missed visit as soon as possible, counsel the participant on the importance of maintaining the assigned visit schedule, and ascertain if the participant wants to or should continue in the study.

- Before a participant is deemed “lost to follow-up”, the Investigator or designee must make every effort to regain contact with the participant: 1) where possible, make 3 telephone calls; 2) if necessary, send a certified letter (or an equivalent local method) to the participant’s last known mailing address, and 3) if a participant has given the appropriate consent, contact the participant’s general practitioner for information. These contact attempts should be documented in the participant’s medical record.
- Should the participant continue to be unreachable, she will be considered to have withdrawn from the study.

8 Study Assessments and Procedures

The visit procedures are described in the Schedule of Activities ([Section 1.3](#)) and [Appendix 4](#).

8.1 Efficacy Assessments

8.1.1 Primary endpoints

Ongoing pregnancy (at 10-12 weeks of pregnancy [8-10 weeks after ET]). Ongoing pregnancy is defined in [Section 9.4.1.1](#).

8.1.2 Secondary endpoints:

- β-hCG positive
- Implantation
- Clinical pregnancy
- Early abortion
- Bleeding (luteal phase, vaginal)
- The safety profile of the study intervention will be assessed according to [Section 8.2](#).

The definitions are provided in [Section 9.4.1.2](#).

8.2 Safety Assessments and Procedures

The safety profile of the study intervention will be assessed through the recording, reporting and analysis of baseline medical conditions, AEs, physical examination findings and laboratory tests.

Comprehensive assessment of any potential toxicity experienced by each participant will be conducted starting when the participants give informed consent and throughout the study. The Investigator will report any AEs, whether observed by the Investigator or reported by the participant; the reporting period is specified in [Section 8.3.1](#) (Time Period and Frequency for Collecting Adverse Event and Serious Adverse Event Information).

8.2.1 Physical Examinations

- A brief physical examination will include, at a minimum, assessments of the skin, lungs, cardiovascular system, and abdomen (liver and spleen).
- Investigators should pay special attention to clinical signs related to previous serious illnesses.

8.2.2 Vital Signs

- Vital signs will be measured in a semi-supine position after 5 minutes rest and will include temperature, systolic and diastolic blood pressure, and pulse

8.3 Adverse Events and Serious Adverse Events

The definitions of an AE and a SAE are in [Appendix 3](#).

8.3.1 Time Period and Frequency for Collecting Adverse Event and Serious Adverse Event Information

The AE reporting period for safety surveillance begins upon endometrial transformation (Visit 2) and continues until the End of Study Visit.

Any SAE assessed as related to study intervention must be recorded and reported, as indicated in [Appendix 3](#), whenever it occurs, irrespective of the time elapsed since the last administration of study intervention.

The method of recording, evaluating, and assessing causality of AEs (including SAEs) and the procedures for completing and transmitting SAE reports are in [Appendix 3](#).

8.3.2 Method of Detecting Adverse Events and Serious Adverse Events

At each study visit, the participant will be queried on changes in his or her condition. During the reporting period, any unfavorable changes in the participant's condition will be recorded as AEs, regardless if reported by the participant or observed by the Investigator.

Complete, accurate and consistent data on all AEs experienced for the duration of the reporting period (defined below) will be reported on an ongoing basis in the appropriate section of the CRF. All SAEs must be additionally documented and reported using the appropriate Report Form as specified in [Appendix 3](#).

8.3.3 Follow-up of Adverse Events and Serious Adverse Events

AEs are recorded and assessed continuously throughout the study, as specified in [Section 8.3.1](#) (Time Period and Frequency for Collecting Adverse Event and Serious Adverse Event Information) and are assessed for their outcome at the End of Study Visit. All SAEs ongoing at the End of Study Visit must be monitored and followed up by the Investigator until stabilization or until the outcome is known, unless the participant is documented as "lost to follow-up". Reasonable attempts to obtain this information must be made and documented. It is also the responsibility of the Investigator to ensure that any necessary additional therapeutic measures and follow-up procedures are performed. Further information on follow-up procedures is given in [Appendix 3](#) (Adverse Events: Definitions and Procedures for Recording, Evaluating, Follow-up, and Reports).

8.3.4 Regulatory Reporting Requirements for Serious Adverse Events

The Sponsor will send appropriate safety notifications to Health Authorities in accordance with applicable laws and regulations.

The Investigator must comply with any applicable site-specific requirements related to the reporting of SAEs (particularly deaths) involving study participants to the Independent Ethics Committee (IEC)/ Institutional Review Board (IRB) that approved the study.

In accordance with International Council for Harmonization (ICH) Good Clinical Practice (GCP), the Sponsor/designee will inform the Investigator of findings that could adversely affect the safety of participants, impact the conduct of the study or alter the IEC's/IRB's approval/favorable opinion to continue the study. In line with respective regulations, the Sponsor/designee will inform the Investigator of AEs that are both serious and unexpected and considered to be related to the administered product ("suspected unexpected serious adverse reactions" or SUSARs). The Investigator should place copies of Safety Reports in the Investigator Site File. National regulations regarding Safety Report notifications to Investigators will be considered.

When specifically required by regulations and guidelines, the Sponsor/designee will provide appropriate Safety Reports directly to the concerned lead IEC/IRB and will maintain records of these notifications. When direct reporting is not clearly defined by national or site-specific regulations, the Investigator will be responsible for promptly notifying the concerned IEC/IRB of any Safety Reports provided by the Sponsor/designee and of filing copies of all related correspondence in the Investigator Site File.

For studies covered by the European Directive 2001/20/EC, the Sponsor's responsibilities regarding the reporting of SAEs/SUSARs/Safety Issues will be carried out in accordance with that Directive and with the related Detailed Guidance documents.

